Feasibility of Home-based Exercise Program for Adults With Cystic Fibrosis

Identifiers: NCT05239611 Unique Protocol ID: STUDY00146919

Date August 5th 2024

This was a randomized controlled pilot and feasibility study or a home-based exercise program among PwCF. Participants were recruited from The University of Kansas Health System (TUKHS) CF outpatient clinic. All study procedures were approved by the University of Kansas Medical Center Institutional Review Board and written informed consent was obtained from all participants (IRB number CR00020120).

Participants

Adults with CF (two confirmatory CF mutations or sweat chloride > 60 mmol/L) who were 18 years of age or older and stable on HEMT elexacaftor/tezacaftor/ivacaftor (ETI) for ≥ 3 months with clearance from their CF physician were eligible to participate. Exclusion criteria included completion of ≥ 150 minutes of structured exercise per week for the last X time, pregnancy, post solid organ transplant, active treatment for mycobacterial infections, oxygen dependent at rest or with exercise, $\text{FEV}_1 < 40\%$ of predicted, clinical evidence of cor pulmonale, untreated arterial hypertension (resting systolic blood pressure > 140 mm Hg, diastolic blood pressure > 90 mmHg), systolic blood pressure less than 90 mm Hg while standing, congestive heart issues, active treatment for Allergic Bronchopulmonary Aspergillosis (ABPA), pulmonary exacerbation within 4 weeks prior to Day 1, or changes in therapy (including antibiotics) for pulmonary disease within 4 weeks prior to Day 1, significant hemoptysis within 4 weeks prior to Day 1 (≥ 5 mL of blood in one coughing episodes or > 30 mL of blood in a 24 hours period), and ongoing participation in an investigational drug study within 60 days prior to Day 1.

Eligible participants who consented were randomized 1:1 via a computer-generated randomization technique to either the intervention or control group. Participant demographics, incremental meter shuttle walk test (IMSWT), spirometry, xenon magnetic resonance imaging (Xe-MRI), the Cystic Fibrosis Questionnaire Revised (CFQ-R), and surveys regarding physical activity were completed at baseline and upon study completion. Semi-structured interviews evaluating exercise were completed in the intervention group at the conclusion of the follow-up visit.

Intervention/Exercise Protocol

Those randomized to the intervention group were assigned to an exercise coach and asked to wear a wrist-worn Garmin vivosmart 4 actigraph during physical activity. Participants were asked to complete 12 weeks of progressive home-based exercise program in a target heart rate zone, with an exercise target of 60 minutes in weeks 1 and 2, 90 minutes in weeks 3 and 4, 120 minutes in weeks 5 through 8, and 180 minutes in weeks 9 through 12. Target heart rate zone was calculated using the heart rate reserve (HRR) method for moderate activity levels as described by the American College of Sports Medicine (ACSM), which uses an intensity factor of 40-85% of the maximal heart rate achieved during the IMSWT. Exercise coaches contacted participants weekly by phone, text, or email to discuss

strategies for reaching exercise minute goals and provide personalized feedback regarding exercise motivations and barriers. Physical activity was participant-determined and based on individual preferences, lifestyle, and resource availability.

The control group received standard-of-care instructions regarding exercise and instruction on how to access beamfeelgood, an online repository of exercise videos available free of charge for PwCF.

Outcome Measures

The IMSWT was used as a surrogate for CR-fitness as it has shown construct validity and predictive value for $VO_{2\text{max}}$ in adult CF patients. Testing was conducted according to the protocol outlined by Singh et al. Distance and maximal heart rate were collected at the end of the IMSWT.

Adherence to exercise was calculated as the number of exercise minutes completed in the target heart rate zone each week/weekly target exercise minutes. Participants were considered to be adherent if they completed $\geq 70\%$ of weekly exercise minutes for $\geq 70\%$ of the 12-week intervention.

Spirometry was obtained from TUKHS CF outpatient clinic. Forced expiratory flow in one second (FEV1) was collected from TUKHS electronic medical record. FEV1 is expressed as %predicted (ppFEV1) using NHANES III spirometric reference ranges.

The CFQ-R is a valid and reliable self-administered questionnaire composed of 44 items on 12 generic and disease-specific domains and is used to assess health-related quality of life (HrQoL) in adults with CF. (citation) Overall CFQ-R score and each domain score were collected.

The Barriers to Physical Activity questionnaire assesses barriers to participating in physical activity and asks participants to rank 15 items on a 5-point Likert scale from “never” to “very often” limiting physical activity. Overall barrier score and each item score were collected.

Xe-MRI was used to measure ventilation and gas exchange. Xe-MRI was completed prior to the IMSWT for all study participants by a minimum of 30 minutes. Isotopically enriched (90% ^{129}Xe) xenon gas (Linde Specialty Gases) was polarized to $>25\%$ using a Polarean 9820 xenon hyperpolarizer (Polarean Imaging Plc., Durham, NC). The total dose volume delivered to participants was equal to 20% of FVC measured at the baseline study visit. Participants were imaged using a 3T Skyra MRI scanner (Siemens, Erlangen, Germany) using a flexible transmit/receive ^{129}Xe vest coil (Clinical MR Solutions, LLC, Brookfield, WI). Calibration data was analyzed in real-time using a home-built MATLAB (version 2020A, MathWorks, Natick MA) program and the outputs used for subsequent imaging. Following calibration, every participant was imaged using 3D ventilation imaging. Within the same breath, a

geometry-matched ^1H anatomic image set was acquired to be used for image quantification.

Xe-MRI images were quantified using an automated pipeline to quantify ventilation defect percent (VDP). VDP was calculated using the mean anchored linear binning approach with a threshold of 60%. VDP was an exploratory endpoint for this study.

Data Analysis

To achieve 80% power at an α level of 0.05 (two-sided), 12 participants were needed in each group to detect an effect size of 1.2. A target enrollment of 15 per group ($n=30$ total) was set to account for attrition.

Data is presented as mean \pm SD, categorical data is presented as a percentage. Baseline between group differences were analyzed with a Wilcoxon Mann-Whitney test for continuous variables and a Fisher's exact test for categorical variables, as appropriate. No between group differences were found for demographic or baseline measures. Group differences for all outcome measures were assessed using a Wilcoxon Mann-Whitney test. An intention-to-treat approach was used for participant baseline characteristics. Participants with missing post-intervention data were excluded from group difference analyses.

All statistical analyses were performed using SAS v9.4. All comparisons were two-sided with the level of significance set at $p < 0.05$.

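### The stated 80% power at 12 per group fits a two-sample t-test; for normal data the planned Wilcoxon Mann-Whitney test gives about 76.5%

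*Combined protocol and SAP*

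**What the plan says.** The opening paragraph describes the design: "This was a randomized controlled pilot and feasibility study". The rest is in the Data Analysis section.

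- **Sizing.** The target is introduced with "To achieve 80% power" at two-sided 0.05, and the result is that "12 participants were needed in each group to detect an effect size of 1.2". The section does not name the test, the outcome, its standard deviation or the assumed distribution.
- **Attrition.** "A target enrollment of 15 per group" is set to allow for losses. Going from 15 to 12 is an allowance of 3 per group, or 3/15 = 20%.
- **Analysis.** "Group differences for all outcome measures were assessed using a Wilcoxon Mann-Whitney test". No other between-group test of outcomes is given.
- **Missing data.** "Participants with missing post-intervention data were excluded from group difference analyses". If the attrition allowance is used up, 12 per group is therefore the analysed number.

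**The concern.** A power figure describes one test under one distribution. Here the figure agrees closely with the standard t-test calculation, while the analysis uses a rank test. For normal data the rank test is somewhat less efficient. With groups this small it also loses power because its null distribution is discrete and its actual size falls below 0.05.

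What is at stake is how a null result is read. At 12 evaluable per group a reader would take the type II error for a true difference of 1.2 to be 20%. For normal data it is 100 − 76.5 = 23.5%.

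**Working it through.** **Inputs.** Power 80%, two-sided 0.05, effect size 1.2, 12 evaluable and 15 enrolled per group, and the Wilcoxon Mann-Whitney test all come from Data Analysis. The allocation comes from Participants ("randomized 1:1 via a computer-generated randomization technique"). Two inputs are assumptions because the document does not supply them: 1.2 is read as a standardised mean difference d, and the outcome distribution is taken as normal first and then varied.

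**Step 1: reproduce the plan's figure.** For a two-sample t-test with n per group, the noncentrality is d·√(n/2) on 2n − 2 degrees of freedom. At n = 12 this is 1.2 × √6 = 2.94 on 22 degrees of freedom, and two-sided power is 80.2%. At n = 11 it is 76.3%. Solving for 80% gives n = 11.94, which rounds up to 12. The stated figure reproduces. A normal approximation would have given 11 per group (83.6% power at 12), and a one-sided t-test has 88.5% at 12, so neither fits as well.

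**Step 2: rejection region of the planned test, 12 v 12.** Under the null, U has mean n²/2 = 72 and standard deviation √(n²(2n + 1)/12) = √300 = 17.32.

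- Exact test: reject at U ≤ 37 or U ≥ 107; actual size 0.0449.
- Normal approximation with continuity correction: lower cut-off 72 − 0.5 − 1.96 × 17.32 = 37.55, hence the same region.
- Normal approximation without correction: lower cut-off 72 − 1.96 × 17.32 = 38.05, hence U ≤ 38 or U ≥ 106; actual size 0.0519.

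**Step 3: power at 12 v 12, normal data, shift of 1.2 SD.**

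| Version of the test or formula | Power |
|---|---|
| Exact, or normal approximation with continuity correction | 76.5% |
| Normal approximation, no correction (size 0.0519) | 78.6% |
| t approximation to the rank statistic | 72.1% |
| Noether's formula | 72.6% |
| t-test with n scaled by 3/π | 78.2% |
| t-test with n scaled by 0.864 (worst case) | 73.6% |

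The first three rows are simulated with 400,000 trials; a further 1,000,000 trials gave 76.6% for the exact test. Simulated t-test power in the same runs was 80.3%, which checks the simulation. Noether's row uses P(Y > X) = Φ(1.2/√2) = 0.802, giving Φ(√(3 × 24) × 0.302 − 1.96) = 72.6%. None of the versions reaches 80%.

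With the exact test at 12 per group, 80% power is reached at d of about 1.25 (79.8% at 1.25, 80.0% at 1.252).

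**Step 4: other distributions.** Exact test, 12 v 12, each distribution scaled to SD 1 and shifted by 1.2, 400,000 simulations each.

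| Distribution | Power |
|---|---|
| Uniform | 71.7% |
| Normal | 76.5% |
| Logistic | 80.2% |
| Gamma, shape 4 | 81.5% |
| t, 5 df | 83.6% |
| Laplace | 84.5% |
| Exponential | 89.1% |

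**Step 5: less attrition.** Exact test, normal data, d = 1.2.

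| Evaluable | Lost of 30 | Power |
|---|---|---|
| 12 v 12 | 6 | 76.5% |
| 12 v 13 | 5 | 78.4% |
| 13 v 13 | 4 | 79.9% |
| 12 v 14 | 4 | 80.3% |
| 12 v 15 | 3 | 81.8% |
| 14 v 14 | 2 | 84.4% |
| 15 v 15 | 0 | 86.1% |

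**The case against.** The strongest reply is that the document does not prove a mismatch. It names no test for the sizing, and the Wilcoxon Mann-Whitney test can also lead to 12: with a logistic outcome its power is about 80% at 12 per group and 77.0% at 11. On that view the numbers are mutually consistent and only a description is missing. The 76.5% also rests on normality, on reading 1.2 as a standardised difference, and on the exact or continuity-corrected test. Five of the seven distributions tried reach 80%. Some of the 3.5-point gap comes from discreteness rather than inefficiency, since the 3/π shortcut alone gives 78.2%. Finally, this is a pilot with 15 per group enrolled, and a type II error for a difference of 1.2 tells the reader little when 1.2 is tied to no outcome.

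Much of this stands. The t-test origin is an inference, the shortfall is conditional, and the practical effect is small. The missing outcome and scale for 1.2 are a real gap, which the restatement should fill.

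It does not rescue the 80%. Nothing in the document points to a logistic outcome, and normality is the conventional assumption behind an unqualified effect size. Under normality every version of the test checked falls below 80%. The version closest to it, 78.6%, exceeds the 0.05 level. The spread from 71.7% to 89.1% across distributions is itself the reason that an unqualified 80% cannot be assigned to this test.

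**Conclusion.** The concern holds and is minor. For normal data and a standardised difference of 1.2, the planned test has about 76.5% power at 12 per group against the 80% stated. Across versions of the test and approximate formulas the figure runs from about 72% to 79%. The conclusion rests on the two assumptions given with the inputs; under heavy-tailed or skewed distributions the claim would be met or exceeded.

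The shortfall matters only if attrition nearly uses up the allowance. With four losses in total (13 v 13 or 12 v 14) power is 80% to within half a point. The design is not undermined; the power statement is inaccurate for the test used under the usual assumption.

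**What to change.** Replace the power sentence with one that matches the analysis, for example:

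> Assuming normally distributed data, 12 evaluable participants per group give the Wilcoxon Mann-Whitney test (two-sided, 0.05) about 76% power for a standardised difference of 1.2 in [outcome and scale used for sizing]; 80% power corresponds to a difference of about 1.25; with all 15 per group evaluable, power is about 86%.

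If the 80% came from a t-test, say so. If a non-normal distribution was assumed, naming it and the resulting power would resolve the point equally well. Only the sponsor can fill the bracket.

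The cost is one sentence and a slightly less favourable figure. The study is written up as completed, so nothing in its conduct or analysis changes, and neither a different test nor more enrolment is proposed.
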